**Prospective Evaluation of Foreign Body Airway Obstruction
Interventions Among Adults and Children: A Non-randomized
Pilot Cohort Study**

STUDY PROTOCOL AND STATISTICAL ANALYSIS PLAN

October 16th, 2025 – Version 1

October 27th, 2025 – Version 2

- Updated sample size calculation, and analysis of effectiveness outcomes.

Objectives

- Primary:
 - To determine the feasibility of prospectively identifying and recruiting patients with foreign body airway obstruction (FBAO) in Alberta, Canada.
- Secondary:
 - To determine the effectiveness and safety of basic life support (BLS) FBAO interventions among different patient age categories experiencing out-of-hospital FBAO

Research Question – Feasibility Study (Primary Objective)

1. What is the rate of eligible FBAO patients recruited per month through prospective identification in Alberta, Canada, and what proportion of satisfactory data collection is obtained?

Research Questions – Future Effectiveness and Safety Studies (Secondary Objective)

1. Among conscious adults and children with an out-of-hospital FBAO, which initial BLS FBAO intervention (abdominal thrusts, back blows or chest compressions) is more effective and safer?
2. Among conscious adults and children with an out-of-FBAO who failed initial management, is continuing the same intervention more effective than changing interventions?
3. Among conscious adults and children with an out-of-hospital FBAO who failed initial management, which BLS FBAO intervention or combination of interventions is more effective and safer?

Methods

Study Design

We will conduct a study to assess the feasibility of identifying and recruiting a prospective cohort of patients who experience an out-of-hospital FBAO in Alberta, Canada. The results of this pilot study will inform a future appropriately powered prospective cohort study examining the effectiveness and safety of FBAO interventions.

We will follow two reporting guidelines to ensure inclusion of all relevant sections:

- Consolidated Standards of Reporting Trials (CONSORT) extension to randomised pilot and feasibility trials [1]
- STROBE (Strengthening the Reporting of Observational Studies in Epidemiology) guideline [2]

The Conjoint Health Research Ethics Board of the University of Calgary (REB25-0419) and Alberta Health Services approved the study.

Setting

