Exposure: Given the primary aim of the feasibility study is a descriptive analysis of the outcome variables, no exposure variable is defined.

Sample Size: Abdominal thrusts and back blows are the two primary FBAO interventions used on adults and children, so the sample size is based on data of these two techniques

[3]. We estimate that 640 patients will need to be recruited to obtain 80% power using a statistical significance of 0.05 and two-sided z-test of independent proportions to detect, with successful proportion of abdominal thrusts and back blows equal to 59.5% and 72.2% respectively, with a ratio of patients who received abdominal thrusts versus back blows equal to 3.5 [3].

To complete an intervention effectiveness study in 48 months, we would need to recruit a mean of 13.3 patients per month. The slowest acceptable recruitment rate would be if recruitment required one additional year to obtain our desired sample size (60 months total). This would require recruitment of 10.6 patients per month. Using the traffic light approach for a feasibility study's sample size, we set the green criterion (progression, no concerns) to 13 patients or more per month and the red criterion (major problems, potentially not remediable concerns) to less than 10 patients per month. The amber zone will be set as 10-13 patients per month, which represents a recruitment rate range that may be compatible with a successful future study; however, we will first aim to identify and address remediable recruitment challenges before deciding whether to proceed [10].

Analysis: We will conduct a descriptive analysis of the recruited cohort's demographics, as well as the FBAO incident situational factors (categorical: frequency and proportions; continuous: medians and interquartile ranges). We will calculate the mean recruitment rate by dividing the number of recruited patients over the entire study period by the number of months recruitment was ongoing. We will track the number of patients who were eligible over the entire study period and determine our proportion of successful recruitment by dividing the count of recruited patients by the count of eligible patients. Finally, among our recruited patients, we will review the data collection forms and determine the number of patients who had 90% or more of variables obtained to ensure satisfactory data collection processes are in place.

Secondary Objectives: Effectiveness and Safety

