- Exposure: Receiving a single BLS FBAO intervention versus an intervention combination (abdominal thrusts [AT], back blows [BB], chest compressions [CC], AT and BB, AT and CC, BB and CC) after an initial 5 attempts

Question Three: Among conscious adults and children with an out-of-hospital FBAO who failed initial management, which BLS FBAO intervention or combination of interventions is more effective and safer?

- Exposure: FBAO intervention combination (abdominal thrusts [AT], back blows [BB], chest compressions [CC], AT and BB, AT and CC, BB and CC)

Analysis: As this pilot study will be underpowered to accurately estimate precision of the outcomes, we will limit reporting of these results to a descriptive analysis. We will include descriptive statistics of the patients' demographics and FBAO incident situational factors for the total study population, as well as stratified by the exposure variable (categorical: frequency and proportions; continuous: medians and interquartile ranges). We will also report descriptively the outcome variables listed above.

We will summarize missingness of all variables to determine appropriateness of imputation for future studies.

We will perform similar analyses for several subgroups: adults (aged ≥ 13 years), children (aged 3-12 years), patients residing in long-term care, patients with limited mobility, and patients who received first intervention with bystanders versus paramedics.

Covariates

Variable Name	Variable Type	Possible Values
Patient		
Age	Continuous	0 - 100
Sex	Categorical	Male, Female, Other
Estimated Patient Weight	Numerical	
Estimated Patient Height	Numerical	
History of Choking	Categorical	Yes, No, Unknown
Medical Comorbidities	Open response	Free Text
Specifically ask: Stroke, Dementia or Alzheimer's, Difficulty Swallowing or Chewing, Parkinson's Disease	List, select all that apply	Any of the specific answers
Pre-FBAO ADL Independence	Categorical	Independent, Dependent, Unknown
If Dependent: Which ADLs require assistance? Which ADLs are completely dependent?	List, select all that apply	Ambulation/mobility, Eating/feeding, Personal hygiene/bathing, Dressing, Toileting
If Limited Mobility: What is their mobility?	Categorical	Walk independent, Uses cane, Uses walker, Uses wheelchair, Limited to bed
Long term care resident	Categorical	Yes, No, Unknown
Situation		
Location	Categorical	Home, Long term care residence, Restaurant, School, Other public place, Unknown

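### Low power is the stated reason for purely descriptive outcome reporting with no confidence intervals, but it justifies leaving out tests, not intervals

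*Combined protocol and SAP*

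**What the plan says.** The Analysis paragraph under Secondary Objectives: Effectiveness and Safety reads: "As this pilot study will be underpowered to accurately estimate precision of the outcomes, we will limit reporting of these results to a descriptive analysis". It then gives the format for categorical variables as frequencies and proportions, overall and stratified by exposure. That sentence concerns demographics and situational factors. The outcomes get one further sentence, which says only that they too will be reported descriptively. Similar analyses follow in several subgroups. No confidence interval is specified for any effectiveness or safety outcome.

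The secondary objective, under Objectives, is "To determine the effectiveness and safety of basic life support (BLS) FBAO interventions among different patient age categories". The matching research questions are headed as belonging to future effectiveness and safety studies. Both Study Design and the Outcomes paragraph say that the pilot will inform later work.

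No pilot sample size is stated. The Sample Size paragraph concerns the later study: "We estimate that 640 patients will need to be recruited to obtain 80% power".

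**The concern.** The stated reason runs the wrong way. Power is a property of a test, so a pilot with low power should not test. Precision can be estimated at any sample size, and imprecise estimates are where an interval helps most. A proportion from a dozen patients and one from several hundred look the same on the page until their intervals are shown.

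Two things are at stake. One is relief in the smaller technique groups, where the observed proportion says little about the true one. The other is safety, where a count of zero carries no visible warning about the injury rate it leaves open. The pilot exists to plan a larger study, and its planners need to know how far to trust these figures.

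A smaller point goes with this. The secondary objective uses the verb *determine*, while the Analysis paragraph concedes that the pilot can only describe.

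**Working it through.** **Inputs, from the Sample Size paragraph**
- Test: "statistical significance of 0.05 and two-sided z-test of independent proportions", 80% power.
- Relief: "successful proportion of abdominal thrusts and back blows equal to 59.5% and 72.2% respectively".
- Split: "ratio of patients who received abdominal thrusts versus back blows equal to 3.5".
- Rates: "we would need to recruit a mean of 13.3 patients per month"; "we set the green criterion (progression, no concerns) to 13 patients or more per month"; red below 10 per month.

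Patient Recruitment and Consent gives the pilot's duration as 6 months.

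**Step 1. Reproduce the plan's figure of 640.** Pooled-variance formula, no continuity correction, back blows as the smaller group, r = 3.5:
- pooled proportion = (0.722 + 3.5 × 0.595)/4.5 = 0.623
- n = [1.96 × sqrt(0.623 × 0.377 × (1 + 1/3.5)) + 0.842 × sqrt(0.722 × 0.278 + 0.595 × 0.405/3.5)]² / 0.127² = (1.077 + 0.437)² / 0.01613 = 142.1
- total = 142.1 × 4.5 = 639.4

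Rounding each group up gives 143 + 501 = 644. Power at 640 is 80.0%. The plan's figure reproduces.

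**Step 2. Project the pilot's size.**
- Low: 10 × 6 = 60
- High: 13.3 × 6 = 80 (the green threshold itself gives 13 × 6 = 78)

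**Step 3. Split at 3.5:1**, assuming that every patient first receives one of the two main techniques.
- 60 patients: back blows 60/4.5 = 13.3, abdominal thrusts 46.7, so about 13 and 47
- 80 patients: back blows 80/4.5 = 17.8, abdominal thrusts 62.2, so about 18 and 62

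**Step 4. Wilson 95% interval for relief.** With p = x/n and z = 1.96, the limits are
[p + z²/(2n) ± z × sqrt(p(1 − p)/n + z²/(4n²))] / (1 + z²/n).

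For 13/18: centre = (0.722 + 0.107)/1.213 = 0.683; half-width = 1.96 × sqrt(0.01115 + 0.00296)/1.213 = 0.192; interval 0.491 to 0.875.

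| Group | 60 patients | 80 patients |
|---|---|---|
| Back blows | 9/13 = 69% (42% to 87%) | 13/18 = 72% (49% to 88%) |
| Abdominal thrusts | 28/47 = 60% (45% to 72%) | 37/62 = 60% (47% to 71%) |

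The counts are the plan's relief rates times the group sizes, rounded. Both of the plan's rates, 59.5% and 72.2%, lie inside either back-blow interval.

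**Step 5. Exact two-sided 95% upper limit for zero injuries**, 1 − 0.025^(1/n).
- 0/13: 24.7%; 0/18: 18.5%
- 0/47: 7.5%; 0/62: 5.8%

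**Step 6. What a comparison could show.** The 95% half-width of the difference is 1.96 × sqrt(0.722 × 0.278/n_BB + 0.595 × 0.405/n_AT), using the unrounded group sizes.
- 80 patients: 1.96 × sqrt(0.01129 + 0.00387) = 24 points
- 60 patients: 1.96 × sqrt(0.01505 + 0.00516) = 28 points

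The difference that the later study is sized to detect is 12.7 points.

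**The case against.** The strongest reply is that a descriptive analysis without tests suits a feasibility pilot, and that the plan says plainly that it is underpowered. No pilot decision depends on these outcomes, because progression rests on the recruitment rate alone. Counts are already planned beside the proportions, so a reader could work out the intervals. Description also does not forbid intervals. All of this stands, and it limits the weight of the point. It does not rescue the stated reason, which points away from intervals, and it leaves the SAP without any.

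It may also be said that intervals set beside each technique invite the comparison that the pilot should avoid. That is a fair worry. A sentence disclaiming comparative conclusions meets it better than leaving the intervals out.

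Several stronger readings are tempting, and the documents do not support them:
- **That the pilot claims to settle effectiveness.** The objective's verb suggests it, but the heading over the research questions and the Outcomes paragraph assign those questions to future studies. This is a mismatch of wording.
- **That outcomes will certainly be tabulated by technique.** This is a natural reading, since each question is defined by an exposure, but the outcome sentence does not mention stratification. Any count of table cells across exposures and subgroups would rest on that inference.
- **That all groups will be tiny.** Only back blows and rarer groups fall to about 18 or fewer. The abdominal-thrust group is projected at about 47 to 62.
- **That readers will take the tables as findings.** That is a prediction about readers, not an error in the plan.

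**Conclusion.** The point holds in a limited form. The plan gives low power as its reason for description only and specifies no interval for relief, survival, neurological outcome or injury. That reason supports omitting tests and nothing more. In the back-blow group the missing intervals would span about 39 points (13/18) to 45 points (9/13) for relief, and zero injuries would leave rates of 18.5% to 24.7% open.

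These sizes rest on three assumptions: a pilot of 60 to 80 patients, projected from the recruitment thresholds; every patient receiving one of the two main techniques at 3.5:1; and relief near the plan's own rates. Recruitment in the red zone, or any use of chest compressions or other techniques first, would make the back-blow group smaller and its intervals wider. The documents do not give the sizes of the rarer groups or the subgroups.

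This is a cheap improvement to the SAP. It does not threaten the primary feasibility objective, and it is no argument for adding hypothesis tests.

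**What to change.** In the Analysis paragraph under Secondary Objectives: Effectiveness and Safety:
1. Report each effectiveness and safety proportion as n/N with a Wilson or exact 95% interval, and state that no hypothesis tests will be done. Give low power as the reason for omitting tests only.
2. Say whether outcomes are tabulated by exposure, overall and in the subgroups.
3. State that the pilot draws no comparative conclusion between techniques.

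Under Objectives, change *determine* to *describe* in the secondary objective as it applies to the pilot, and leave the stronger verb to the later study.

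The cost is SAP wording, slightly longer tables and a more modest objective. No extra data are needed. One practical step: injuries are collected as free text, so they must be classed as any or none before a proportion and its interval can be given.
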